While much is known regarding the dermal changes that occur with skin aging⁸, there has been little research in the role that keratins and epidermis play in skin aging and the associated skin fragility. It is also not know whether UV exposure has an effect on epidermal keratins. By assessing the epidermal structure of the skin from both photoprotected and photoexposed sites from individuals before and after the application of sulforaphanes, and before and after acute UV light exposure, we hope to understand whether differences exist in the expression of keratins between photoprotected and photoexposed areas and whether sulforaphane can change these differences.

4. Study Procedures

a) Study design, including the sequence and timing of study procedures

Recruitment: Individuals will be recruited from patient populations seen at the general dermatology clinics of Johns Hopkins Department of Dermatology or from patient populations participating in Johns Hopkins Cutaneous Translational Research Program (CTReP) research studies. Interested study participants will be evaluated after their routine clinical care visits. Participants will also be recruited from other patient populations in the Johns Hopkins Health System through the use of flyers. Study procedures will be conducted at the Johns Hopkins CTReP office located at the Johns Hopkins Outpatient Center. Recruitment may include Johns Hopkins University employees or students but these groups will not be specifically targeted for participation. Interested individuals will be interviewed to see whether they meet the basic eligibility criteria to participate in the study. Once eligibility has been demonstrated, the potential subjects will be instructed to make their first study appointment. We will recruit up to 50 participants over the age of 18 with healthy skin and they will be split into 2 groups: Group A) 20 volunteers that will apply sulforaphane in jojoba oil for up to 7 consecutive nights and have biopsies before and after on both photoprotected and photoexposed areas and jojoba oil only only to photoexposed areas for up to 7 consecutive nights with biopsy after 7 days Group B) 20 volunteers that will have 2 test areas irradiated with UV light and biopsies before and 24 hours after UV light irradiation; one of the UV treated areas will be pre-treated with sulforaphane for up to 7 consecutive nights and the other UV treated areas will be pre-treated with jojoba oil.

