Once informed consent is obtained, investigators will identify 2 suitable test areas on the photoprotected upper inner arm for study. Test area dimensions will be about 17 x 17 mm in diameter, the spot size produced by the department's UV device. Each participant will receive up to 7 ml of broccoli sprout extract (BSE) in jojoba oil, containing 3500nmol of sulforaphane and up to 7 ml of jojoba oil only 500 nmol of sulforaphane will be applied each night to Test Area #1 for up to 7 consecutive nights. Additionally, jojoba oil only will be applied each night to Test Area #2 for up to 7 consecutive nights. Areas will be occluded with saran wrap every night. A demonstration and verbal instructions for how and where to apply study drug will be provided to subjects. Clinical assessment and elasticity measurements will be performed during this visit as well.

Visit 2:

UV Light Irradiation: Within 1 to 7 days of BSE and jojoba oil only application, investigators will deliver a fixed dose of UV light to Test Area #1 and Test Area #2. Subjects will be asked to return on-site up to 3 days after UV exposure for biopsy.

Visit 3:

During this visit, investigators will perform clinical assessment, elasticity measurements and three 6 mm punch, one from each Test Area and one from normal, unirradiated skin, also on the upper inner arm, to serve as a control.

Visit 4:

Subjects will return on-site 10-14 days after biopsy to have sutures removed.

Photography: Standardized digital photographs will be obtained by study staff using a digital camera and software under standard photographic conditions at each study visit. Participants' eyes will be blacked out to de-identify facial photos. Photograph files will be coded to remove personal identifiers and stored on a secure hard drive in CTReP.

Clinical assessment: Clinical assessments will be performed to 1) record baseline skin findings 2) to identify up to 4 suitable areas for biopsy, 3) give information/demonstration about sulforaphane application and 4) to identify occurrence of any adverse events.

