Skin biopsies: up to five skin punch biopsies (up to 6 mm in diameter) from Group A will be taken in order to conduct the laboratory work. Two from the untreated control areas, two after up to 7 days applying sulforaphane, and one after up to 7 days applying jojoba oil only to a photoexposed site. Up to three skin punch biopsies (up to 6 mm in diameter) from Group B will be taken in order to conduct to the laboratory work. One from control area, one from UV irradiated area after topical jojoba oil only and one from UV irradiated area after topical sulforaphane. All areas will be biopsied using standard punch biopsy tools and following standard clinical protocols, including cleansing the skin with an alcohol wipe and injecting local anesthesia with lidocaine and epinephrine. No more than five total skin biopsies will be obtained from a volunteer over the course of the study. After removal of the tissue sample, one or two sutures are placed to close the circular opening. Sutures are removed and a scar is formed, but typically heals well without complications and blends well with the surrounding skin. Routine post-biopsy care instructions will be provided and volunteers will be instructed to return in 10 to 14 days to have sutures removed and for assessment of healing.

Laboratory studies: Tissue work-up may include but not limited to cryosectioning and immunofluorescence staining and protein or RNA extraction for molecular assays (RT-PCR and/or qPCR for select mRNAs and western blotting for select protein antigens). The levels of keratin 1, keratin 5, keratin 10, keratin 14, keratin 16, keratin 17, and Nrf2 will be studied with both immunofluorescence and RNA PCR. [name] laboratory from the Department of Biochemistry and Molecular Biology and Bloomberg School of Public Health at Johns Hopkins University has successfully applied this strategy.

b. Study duration and number of study visits required of research participants.

The study consists of up to 4 on-site study visits within a 3 week period, including the suture removal visit. We will allow 4 years to complete the study.

c. Blinding, including justification for blinding or not blinding the trial, if applicable. NOT APPLICABLE

d. Justification of why participants will not receive routine care or will have current therapy stopped.

NOT APPLICABLE

e. Justification for inclusion of a placebo or non-treatment group. NOT APPLICABLE

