Skin elasticity measurements will be obtained using a cutometer (Cutometer® MPA 580) and a ballistometer (Dia-stron Limited Dermal Torsional Ballistometer). The only stimulus to the participant via cutometer is a light vacuum suction of the skin via a 6mm diameter probe. The resistance of the skin to be sucked up by negative pressure (firmness) and its ability to return into its original position (elasticity) are displayed as curves. The accompanying software allows us to calculate different parameters like the ability of the skin to return to its original state and the tiring effects of the skin after repeated suction. The ballistometer probe lightly taps the skin and bounces repeatedly on the test site before coming to rest. An optical sensor monitors the position of the probe and the positional data is transmitted to the PC software. It does not cause any discomfort to the subject, but offers measurements of skin firmness and dynamic resilience of skin. Both devices are non invasive and have been approved by the Department of Clinical Engineering.

The UVB light radiation will be administered using the Lumera Targeted Phototherapy system (Daavlin, Bryan OH, USA). Buttock skin will be irradiated using a hand-held fiber optic cable with an adjustable aperture size. The JHU Department of Dermatology has already purchased this device and it has been approved by the Department of Clinical Engineering. The device has an emission spectrum in the ultraviolet B range of 290-320 nm. This device is FDA approved for the treatment of several dermatologic diseases, such as psoriasis, seborrheic and atopic dermatitis, and vitiligo, and can be safely used on all skin types (I-VI). The system consists of a light source, a spot handpiece, and a light guide that connects the handpiece to the light source. The light source has a timer and an output level control to adjust the intensity of the ultraviolet light. The device will be calibrated using a manufacturer-provided UV meter prior to every use to ensure accurate doses of ultraviolet light.

7. Study Statistics

We are collaborating with researchers from the Department of Biochemistry and Molecular Biology and Bloomberg School of Public Health at Johns Hopkins University. The skin biopsies will be analyzed by immunofluorescence staining and molecular analyses for keratin 1, keratin 5, keratin 10, keratin 14, keratin 16, keratin 17, and Nrf2 activation.

8. Risks

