It is possible that there will be skin irritation of the skin. Risks include irritant dermatitis and/or contact dermatitis, itching sensations from the sulforaphane. Risk events, problems, and deviations will be immediately reported by the PI to the IRB.

Risks include potential bleeding and a slight risk of infection from the punch biopsies. As with any cut in the skin, a scar will develop, although its appearance will likely fade over time. We will screen carefully for keloids in our exclusion criteria, but in rare individuals with no prior keloid history, keloids or excessive scarring may develop at the biopsy site. As with any biopsy, there is a risk of pain or discomfort from the procedure.

There are no anticipated risks or discomforts associated with gross mechanical measurements of elasticity.

There is a risk of sunburn from the UV treatment, although the risk is minimal given the small area affected and limited numbers of treatments. There is a risk of ultraviolet injury to the eyes. Both the operator and subjects will wear UV blocking protective eyewear provided by the device manufacturer. The provided eyewear meets the ANSI Z87.1-2003 standard and blocks 99.9% of UV in wavelengths 180-380 nm and has wrap-around side shields. In addition, the treatment area is the buttock, so even inadvertent eye exposure is highly unlikely.

In terms of confidentiality, there are minimal risks as all study participant information will be de-identified. Since this is an exploratory study, no confidential or protected information would be taken outside of the standard. There is a slight financial risk to the participants in the rare event that the above complications occur requiring additional medical care.

9. Benefits

There will be no direct benefit to the participant as a result of this study. Instead, the potential benefit will be to society at large. We hope to better understand the differences on keratins' expression on phototexposed and photoprotected skin, after acute UV light exposure and also if sulforaphane can play a role on this expression and on skin elasticity.

10. Payment and Remuneration

Study participants who undergo all study procedures, including correct application of sulforaphane, non-invasive measurements, UV light irradiation (if in Group B) and biopsies (up to 5 for Group A and up to 3 for Group B) will receive a total of \$100 at completion of the study.

11. Costs

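### The device and risk sections name the buttock as the UV site while Group B is treated, irradiated and biopsied on the upper inner arm, and the visit schedule leaves the post-UV biopsy time open

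*Combined protocol and SAP*

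**What the plan says.** **Site.** In Section 4a, Group B, Visit 1, "investigators will identify 2 suitable test areas on the photoprotected upper inner arm for study". Test Area #1 then receives sulforaphane and Test Area #2 jojoba oil. At Visit 2, "investigators will deliver a fixed dose of UV light to Test Area #1 and Test Area #2". At Visit 3 three punch biopsies are taken, "one from each Test Area and one from normal, unirradiated skin, also on the upper inner arm, to serve as a control".

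Section 6 (Drugs/ Substances/ Devices) gives another site: "Buttock skin will be irradiated using a hand-held fiber optic cable with an adjustable aperture size". Section 8 (Risks) agrees with Section 6 and uses the site in its eye-safety argument: "the treatment area is the buttock, so even inadvertent eye exposure is highly unlikely". Section 8 also requires eyewear that "blocks 99.9% of UV in wavelengths 180-380 nm and has wrap-around side shields".

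**Timing.** The design summary in Section 4a describes Group B as having "2 test areas irradiated with UV light and biopsies before and 24 hours after UV light irradiation". The Visit 2 entry instead asks participants to come back for biopsy within 3 days of irradiation, with no target time and no lower limit.

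**Which biopsies.** The Skin biopsies paragraph in Section 4a lists the Group B specimens: "One from control area, one from UV irradiated area after topical jojoba oil only and one from UV irradiated area after topical sulforaphane".

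**The concern.** The protocol names two body sites for one UV exposure. If the device section were followed literally, the irradiated skin would have had neither oil and the pre-treated skin would have had no UV. The comparison of UV alone with UV after sulforaphane, which is the secondary objective in Section 2, could not then be made. If the buttock text is a leftover, the science survives, but the device description and part of the risk argument given to the IRB concern a site that is not treated.

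The timing is a looser matter. Keratin expression after UV may depend on the time since exposure. If participants return at different times, the average difference between irradiated and unirradiated skin belongs to no defined time point. The Group B elasticity readings at Visit 3 share the same open window. Section 7 describes no analysis that would adjust for hours since UV, and nothing in the protocol asks for those hours to be recorded.

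**Working it through.** **1. Site, by place in the protocol**

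| Place | Site |
|---|---|
| 4a, Group B Visit 1: test areas and both oils | upper inner arm |
| 4a, Visit 2: UV dose | Test Areas #1 and #2, so upper inner arm |
| 4a, Visit 3: three biopsies, including the control | upper inner arm |
| 6: device | buttock |
| 8: eye risk | buttock |

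The schedule is consistent within itself. Two statements, in two different sections, disagree with it, and no text says that both sites are used or that one replaces the other.

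**2. Eye safeguard.** The device emits 290-320 nm (Sections 4a and 6). The eyewear covers 180-380 nm (Section 8). The first range lies inside the second, so this protection does not depend on body site.

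**3. Group B biopsies by visit.** Visit 1: 0. Visit 2: 0. Visit 3: 2 irradiated + 1 unirradiated = 3. Visit 4: 0. No biopsy precedes irradiation, so the design summary's mention of one is loose. The comparator is the concurrent unirradiated arm specimen.

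**4. Timing.** The plan gives 24 hours in one place and up to 3 × 24 = 72 hours in the other. These are compatible, because 24 hours falls inside the window, but the schedule does not fix the time.

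The documents give no time course and no SD, so the size has to be shown over an assumed range:

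- n = 20 (Group B, Section 4a).
- The SD of the within-person irradiated-minus-unirradiated difference at a fixed time is set to 1.
- D is the change in the mean of that difference from 24 to 72 hours, in those SDs, and is taken as linear.
- One third of participants are biopsied at each of 24, 48 and 72 hours, giving offsets of 0, D/2 and D.

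Formulas:

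- Shift of the average from its 24-hour value: (0 + D/2 + D)/3 = D/2.
- Added variance: [(D/2)² + 0 + (D/2)²]/3 = D²/6.
- Fixed-time standard error (SE): 1/√20 = 0.224.
- SE multiplier: √(1 + D²/6).

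| D | Shift (SD) | Shift ÷ 0.224 | SE multiplier |
|---|---|---|---|
| 0 | 0 | 0 | 1.000 |
| 0.5 | 0.25 | 1.12 | √1.0417 = 1.021 |
| 1 | 0.50 | 2.24 | √1.1667 = 1.080 |
| 2 | 1.00 | 4.47 | √1.6667 = 1.291 |

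Twenty people cannot be split exactly into thirds. A 7/7/6 split gives a shift of (7 × 0 + 7 × D/2 + 6 × D)/20 = 0.475D instead of 0.5D, which changes nothing of substance.

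**The case against.** The best case for leaving this as a minor point runs as follows. The visit schedule is the operative text and is unambiguous. Staff who follow it would irradiate the labelled, pre-treated arm areas, so what remains is one stale sentence on the device and one supporting sentence on risk. The eyewear is the main safeguard and works at any site. The 24-hour statement lies within the 3-day window, so there is no contradiction on timing. Section 8 calls the study exploratory, and Section 7 states no hypothesis test. The size rests on an assumed D, linearity and visit pattern, and it runs from no effect to 4.5 SEs.

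Much of this stands. Irradiation of the buttock is unlikely in practice, the timing texts are compatible, and the table only illustrates a range and cannot say which value of D applies. The 24-72 hour model also omits earlier biopsies, which the schedule permits.

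One further point is fair. The sulforaphane and jojoba specimens come from the same person at the same visit, so unequal timing cannot bias one against the other. But if sulforaphane's effect on the UV response changes with time, the average of that contrast is also taken over a mix of times.

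None of this removes the conflict. The buttock appears in the device procedure and in a participant-safety argument, and a risk description should name the skin that is treated.

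**Conclusion.** The concern holds and should be fixed. The site conflict is an internal inconsistency in current text: two statements against a schedule that places both pre-treated areas and all three Group B biopsies on the upper inner arm. Its likely consequence is a wrong description to the IRB, not wrong irradiation, and the eyewear protection is unaffected.

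The open biopsy window mainly costs interpretation. Under the assumptions in the working, the average UV effect moves by half of whatever change occurs between 24 and 72 hours. The loss of precision is small (2% for D = 0.5, 8% for D = 1) unless the change is large (29% for D = 2). If the effect is flat over that period, there is no cost. Reading the shift as an error also assumes that 24 hours is the intended time, as the design summary says. The primary objective, which rests on Group A, is not affected.

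**What to change.** - **Section 6:** replace the buttock with the upper inner arm as the irradiated site.
- **Section 8:** make the same correction, and rest the eye-risk statement on the eyewear and the targeted spot handpiece.
- **Section 4a, Group B schedule:** set the Visit 3 biopsies at 24 hours after UV with a narrow stated window, and record the actual hours from irradiation to biopsy for each participant.
- **Section 4a, design summary:** replace the reference to a pre-UV biopsy with the concurrent unirradiated upper inner arm control taken at Visit 3.

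The cost is a wording amendment in four places, including a corrected risk sentence for the IRB. Visit 3 would have to follow Visit 2 by one day, which makes scheduling slightly less flexible. No extra biopsies or participants are needed.

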Jojoba oil was chosen based on its known lipophilic nature and ability to permeate deeply into skin ⁹. In a prior study performed in SKH-1 hairless mice (which feature thicker epidermis, more akin to human than furry mouse strains), topical sulforaphane induced K16 and K17 best when administered in jojoba oil. Dermabase, another widely used vehicle, was also tested in this study; however, as Dermabase was found to induce K16/K17 alone even without sulforaphane

added, it was deemed not to be an appropriate vehicle to measure the effects of sulforaphanecontaining broccoli sprout extract.¹⁰

The equivalent of 500nmol of sulforaphane (delivered in the form of broccoli sprout extract) was chosen as the dosage to be used as it has been previously been shown to be tolerable to human skin up to a dose of 681nmol when it caused a transient 3mm erythematous macule.¹⁰ By using jojoba oil coupled with occlusion under saran wrap, we hope to demonstrate penetration of broccoli sprout extract's effect to the basal layer of the epidermis. Broccoli sprout extract is a natural substance that has been orally ingested for thousands of years. It has been used topically and orally with no adverse events.⁹⁻¹¹

Lidocaine with epinephrine will be used as a local anesthetic to the biopsy sites prior to the biopsy procedure. The drug used in the study will be the same drug provided for the entire Johns Hopkins Department of Dermatology. There will not be a separate batch of this drug for the sole purposes of this study as this study is not a clinical trial and use of the drug is unlikely to interfere with study results.

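### Section 10 ties a single $100 payment at completion to correct self-application of sulforaphane, and Group B lists no clinical assessment between first application and UV: a cheap improvement

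*Combined protocol and SAP*

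**What the plan says.** Section 10 (Payment and Remuneration) describes a single total of $100, given at completion, for "Study participants who undergo all study procedures, including correct application of sulforaphane, non-invasive measurements, UV light irradiation (if in Group B) and biopsies". It does not define correct application. It does not say what is paid to someone who stops early, misses nights or is removed.

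Section 4a leaves nightly application under occlusion to the participant, after a demonstration and spoken instructions. Seven nights is a maximum; no minimum is set. Section 4f asks participants to contact staff at once about any reaction and lets the investigator remove participants at discretion.

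For Group B, the only procedure under the Visit 2 heading is irradiation: "Within 1 to 7 days of BSE and jojoba oil only application, investigators will deliver a fixed dose of UV light". The next visit is timed loosely: "Subjects will be asked to return on-site up to 3 days after UV exposure for biopsy". One stated purpose of a clinical assessment, wherever one is listed, is "4) to identify occurrence of any adverse events". Photographs have a wider rule: "Standardized digital photographs will be obtained by study staff using a digital camera and software under standard photographic conditions at each study visit".

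**The concern.** Whether the product was applied correctly will be known largely from what the participant says. If being paid is linked to that answer, and reporting a reaction may end participation, a participant can reasonably think that silence is the safer course. A Group A participant may have given biopsies before the first application, so there is already something to lose.

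What is at stake is participant safety and the accuracy of the tolerability and exposure record. Someone who says nothing may go on applying under occlusion, and in Group B the same skin then receives UV. Section 8 lists irritant or contact dermatitis and itching from sulforaphane, and says of UV: "There is a risk of sunburn from the UV treatment". The one human skin reaction to topical sulforaphane that Section 6 describes was brief: the product was "tolerable to human skin up to a dose of 681nmol when it caused a transient 3mm erythematous macule". A reaction of that kind could be gone by the next visit.

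**Working it through.** The documents give no figure for this point to reproduce, so the check sets the sections side by side and adds a little arithmetic on timing and dose.

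**1. The payment chain.**
- Section 10 makes correct application one of the procedures that must be completed.
- Section 4a gives application to the participant. It describes no diary, returned-product check or visit during the application period.
- Section 4f allows removal after a reported reaction.
- Section 10 is silent on payment after removal.

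Together these create a motive to under-report. They do not state a forfeiture.

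**2. Where clinical assessment is listed (Section 4a).**

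| Point in the study | Group A | Group B |
|---|---|---|
| Before any application | Visit 1: yes | Visit 1: yes |
| After application, before any UV | Visit 2: yes | Visit 2: not listed (UV delivery only) |
| After UV | not applicable | Visit 3: yes |

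The scheduling gap is therefore specific to Group B, and lies between first application and UV.

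**3. Longest time from first application to the next listed assessment.** The assumptions are that application starts on the day of Visit 1 and that the 1-to-7-day window for UV runs from first application.
- Group A: Visit 2 is at day 7 at the latest, so 7 days.
- Group B, with biopsy 24 hours after UV (design paragraph of Section 4a): 7 + 1 = 8 days.
- Group B, with biopsy as late as 3 days after UV (Visit 2 text): 7 + 3 = 10 days.

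If the UV window runs from the last application instead, the Group B times can be longer. These figures count listed assessments only; staff see the test areas when they deliver UV, by day 7 under the same assumption.

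**4. Dose against the cited reaction (Section 6).** 500 / 681 = 0.734, so each nightly dose is about 73% of the dose at which the transient reaction is cited. It is repeated for up to seven nights under occlusion. The protocol does not say whether the 681 nmol was a single dose or over what area it was applied, so the ratio is context and not a risk estimate.

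**5. Procedures already undergone.** In Group A, up to 2 of up to 5 biopsies are taken at Visit 1: 2 / 5 = 40%.

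**6. What cannot be computed.** The documents give no reaction rate, no adherence rate and nothing on how payment affects reporting. Any number for lost reports would be an assumption throughout, so none is offered.

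**The case against.** The strongest reply is that the loss of payment is read into a silence. Section 10 says what people who complete everything receive. It does not say that a reaction, a report of one, a missed night or removal costs the $100. Because seven nights is only a maximum, stopping early is within protocol and need not make application incorrect. The consent form may also provide part payment. All of this stands. It limits the point to an unclear incentive that is easy to remove.

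A second reply is that safeguards exist. Reactions are to be reported immediately, photographs are due at every visit including Group B Visit 2, and "Risk events, problems, and deviations will be immediately reported by the PI to the IRB". This also stands, with limits. The first safeguard is the very self-report that the payment wording may discourage. Photographs cannot show itching or a reaction that has cleared, and their timing relative to UV at Visit 2 is not stated. Reporting to the IRB covers only what staff learn.

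A third reply is that a skin check at Visit 2 detects neither missed nights nor a cleared reaction. That is correct, which is why the check needs a question about reactions and a record of nights applied. That record still relies on self-report, but no longer with money attached.

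A reader might also infer that Group B has no assessment at all before UV. The text does not support that, since Visit 1 lists one. Nor can a reader conclude that redness after UV could not be attributed: Test Area #2 receives jojoba oil, occlusion and the same fixed UV dose in the same person, and so serves as a direct comparator.

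**Conclusion.** The point holds as a minor one. Section 10 as written gives participants some reason not to mention missed nights or a brief reaction, and Group B lists no clinical assessment between first application and UV on the same skin. The size of the behavioural effect is unknown. The conclusion rests on three assumptions: that application is unsupervised (implied by the instructions, not written), that no adherence check exists beyond what is described, and that the consent form does not already provide part payment.

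Two stronger conclusions are tempting and not supported. First, the payment rule does not bias the within-person keratin comparisons. Unmentioned missed nights would make the true dose lower than assumed, but that comes from missing the nights, and reporting them would not restore the dose. Payment for correct application might even improve adherence. Second, the documents do not show that a participant who reacts loses payment; they leave the question open.

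**What to change.** **Section 10.** Pay per completed visit, for example $25 for each of 4 visits (4 x 25 = $100, the same maximum). Remove correct application as a payment condition. State that stopping, or being removed, because of a reaction does not forfeit payment already earned. If the consent form already says this, repeat it here.

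**Section 4a, Group B Visit 2.** List a clinical assessment of both test areas, with a direct question about reactions since Visit 1, before UV is delivered. Record the actual number of nights applied for each area.

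**Cost.** One amendment to wording, one record field per area and a few minutes at an existing visit, with no extra visits or biopsies. The added payment goes to people who do not finish: at most $75 (3 x 25) for someone who misses the last visit, and $100 for someone who attends all four visits without having applied as instructed. The downside is a slightly weaker incentive to complete.
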